1 INTRODUCTION/BACKGROUND

This statistical analysis plan (SAP) describes the data analysis specifications for MicroTransponder, Inc. Protocol MT-St-03 (Stroke) entitled “A Pivotal Randomized Study Assessing Vagus Nerve Stimulation (VNS) During Rehabilitation for Improved Upper Limb Motor Function After Stroke (VNS-REHAB).” This version of the SAP is based on protocol Version 1.1, 23 March 2017.

This SAP follows the International Conference on Harmonisation (ICH) Guidelines E3 and E9. All statistical analyses will be performed using SAS[®], Version 9.4 or higher. Differences in the analyses from those described in the study protocol will be described in Section 5.2 of this document.

This is a pivotal study designed to provide information on the clinical use of vagus nerve stimulation (VNS) during upper limb motor rehabilitation (standard of care) for the treatment of upper limb deficits associated with stroke. The study is proposed as primary support for US market approval; it is expected to give safety and efficacy information.

This Statistical Analysis Plan addresses data collected in Phase I of this study, and is intended to provide safety and efficacy results to support filing for market approval. Data from Phases II and III will then be analyzed separately at a later date.

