2.1 Primary Objective

The primary objectives of this study are to assess:

- the efficacy of VNS therapy compared to standard rehabilitation (active control includes the surgical intervention and sham stimulation) in the recovery of upper limb motor function after stroke.
- safety of the surgical intervention and VNS stimulation

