3 STUDY DESIGN

This protocol is a pivotal study of up to 120 subjects and 15 clinical sites. All subjects are implanted with the Vivistim System[®] and then randomized to either study treatment or active-control treatment. Study treatment is vagus nerve stimulation (VNS) delivered during rehabilitation. Active control treatment is rehabilitation (standard-of-care treatment) with only a minimal amount of VNS at the start of each session intended to support blinding.

This study has three distinct stages:

Stage I – blinded, with consent, assessment, implant, baseline assessment, acute therapy (6 weeks), and follow-up assessment periods (Days 1, 30 and 90 post-acute therapy)

Stage II – unblinded follow-up, including additional therapy sessions and quarterly assessments through one year post implant. Control group subjects crossover to VNS treatment.

Stage III - annual (yearly) follow-up through commercial approval to allow the device to remain implanted and the subject to continue at-home use. Additional rehabilitation sessions are allowed at the investigator's discretion.

This statistical analysis plan (SAP) is focused on Stage I (blinded, randomized portion). A future SAP will focus on Stage II and Stage III, and will be developed prior to the first subject completing Stage II (first subject reaching one-year post implant).

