3.1 Randomization

Subjects will be randomized 1:1 on the day of implant surgery to either the device treatment (rehabilitation and VNS) or control (rehabilitation and Control VNS) groups. An approved, unblinded person at each site accesses the subject's group assignment via an electronic (web-based) system.

Randomization will be stratified by FMA-UE score (20 to ≤ 35 ; >35 to 50), and age (≤ 30 , >30), within each region (North America vs ROW). Therefore, there are eight (8) randomization assignment tables. When a study site (linked to a region) submits the Randomization form with the subject's FMA-UE score, age, the Clinical Discovery Platform (CDP) will assign the next available treatment assignment from the corresponding randomization table.

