3.2 Delivery of VNS Therapy and Treatment Blinding

Subjects in both groups are treated similarly. At each visit, subjects in both groups will receive stimulation via a push-button press for their first 4 rehabilitation movements (4 stimulations), starting at 0.8 mA and reducing in 0.2 mA steps (depending on perception), such that subjects barely perceive or do not perceive the fourth stimulation. This is done to help facilitate blinding.

Thereafter, therapists will continue to use a push-button to initiate stimulation for both groups throughout the therapy sessions; however, only the VNS group receives stimulation. All subjects will be told that they may or may not feel the stimulation during therapy - only about one half of the UK pilot study subjects felt stimulation at 0.8 mA and only about 25% of the subjects in the US IDE study felt 0.8 mA stimulation. Furthermore, subjects in both groups will be told that

they may initially feel the stimulation, but that it is possible that they may acclimate to the stimulation (as also occurred in the UK study and occurs in epilepsy). These efforts, along with the fact that all subjects will receive the same type of rehabilitation and be treated similarly, will help to maintain the blind.

Assessments are performed by a blinded assessor who does not perform therapy on the same subject. A blinded assessor may perform therapy on some subjects and perform assessments on other subjects, but should not perform assessments and therapy on the same subject. Whenever possible, the same assessor should perform the V4, V5, V6 and V7 assessments for a single subject. Sponsor approval is necessary if a different assessor will be used for the same subject at V4 and V5. This separates treatment from assessment and reduces the possibility of an assessor guessing information on group assignment (based on adverse event or subject comment).

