3.3 Study Schedule and Treatment

Stage I: Subjects will be screened and assessed for upper limb paresis associated with stroke using a detailed stroke history evaluation (including type, location, onset, neurological evaluation, etc.) and various assessment scores to determine the level of disability in performing everyday tasks. Clinical evaluations by a stroke expert will confirm subjects entering the study exhibit a moderate to severe motor impairment in the upper extremity (UE) (as indicated by a FMA-UE score of 20 to 50) and have at least a nine-month history of the disorder. After informed consent signature, repeat assessments and other measurements will be recorded prior to randomization. Subjects will maintain their group assignments through Visit 7 (end of Stage I, assessment follow-up).

Subjects will start study therapy after an approximately one-week recovery period after surgery. This time period may vary depending on schedules and subject recovery times. The assessments after surgery, and before treatment (Visit 4) will be the baseline for statistical analyses. After a 6 week acute treatment period, post treatment assessments will be done at Visit 5 (1 Day post treatment), Visit 6 (30 Days post treatment), and Visit 7 (90 Days post treatment). During this 90 day post treatment period, subjects will not receive in-clinic rehabilitation, but are given a magnet to swipe just prior to performing their in-home rehabilitation for 30 minutes daily. The magnet activates VNS in the VNS group subjects but does not activate VNS in the Control subjects.

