3.4 Sample Size Calculation/Justification

The study plan is to enroll and implant up to 120 subjects in order to have approximately 100 subjects complete the study. A sample size of 100 subjects total (50 per group) will have 80% power with 0.05 alpha to detect a difference of 2.3 with SD=4.0 on the FMA UE scale between the two treatment groups. This is based on the assumption of VNS having an average improvement of 7.5 from baseline, with control having an average change of 5.2 from baseline. A sample size of 50 per group will have over 95% power at 0.05 alpha to show a difference in responders (defined as an improvement of 6 points or more from baseline), assuming 75% response in the VNS group and 33% in the control group. With respect to safety, a sample of at least 100 subjects implanted and receiving VNS allows adequate power to detect the incidence of safety and device events. A sample of 100 subjects yields 95% probability that the study will reveal at least one occurrence of all events or complications that occur in subjects at a rate of 3% or greater. In addition, implantation and follow-up of 100 subjects for 6 weeks will yield 4200 subject-days (600 weeks or over 11 years) of total exposure.

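### The 95% chance of seeing a 3% harm in SAP Section 3.4 does not hold for therapeutic-dose stimulation in Stage I, where only about 50 to 60 subjects receive it

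*SAP*

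**What the plan says.** SAP Section 3.4 supports the sample size for safety with three statements:

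- "a sample of at least 100 subjects implanted and receiving VNS allows adequate power to detect the incidence of safety and device events".
- 100 subjects give a 95% probability of observing at least once any event whose rate is 3% or higher.
- "implantation and follow-up of 100 subjects for 6 weeks will yield 4200 subject-days", described there as total exposure.

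Other sections say who is stimulated in Stage I:

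- Section 3.1: "Subjects will be randomized 1:1 on the day of implant surgery".
- Section 3: every subject is implanted, and control treatment is rehabilitation "with only a minimal amount of VNS at the start of each session intended to support blinding".
- Section 3.2: both arms receive four pulses at the start of each visit, from 0.8 mA downwards. After that, "only the VNS group receives stimulation".
- Section 3.3, on the 90 days after therapy: "The magnet activates VNS in the VNS group subjects but does not activate VNS in the Control subjects".

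Section 3 limits this SAP to Stage I and leaves Stages II and III to a later plan. Section 1 says that the Stage I analysis "is intended to provide safety and efficacy results to support filing for market approval". Section 2.1 names as a primary objective the "safety of the surgical intervention and VNS stimulation".

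**The concern.** Section 2.1 sets two safety targets, the operation and the stimulation, but Section 3.4 uses one denominator for both. For the operation and the device the denominator is right. For stimulation at the therapeutic dose, half the subjects in Stage I are not exposed to the treatment whose safety is in question.

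The practical risk lies in how an absence of events is read. From Section 3.4 a reader would conclude that a stimulation harm absent from the results very probably affects fewer than 3% of subjects. If the results are those of Stage I, which are the ones intended for filing, they support that conclusion only at a rate of about 5% to 6%.

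**Working it through.** **Inputs, all from the SAP.**
- Threshold rate 3% and target probability 95% (Section 3.4).
- 100 completers, 50 per group, and up to 120 implanted (Section 3.4).
- Allocation 1:1 (Section 3.1), so up to 120 / 2 = 60 per arm.
- A 6-week course, 42 days (Section 3.4).

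**Step 1. Reproduce the SAP's figures.** The probability of at least one event among n subjects with true rate p is 1 − (1 − p)^n.
- n = 100, p = 0.03: 1 − 0.97^100 = 95.2%. The stated 95% is confirmed.
- Smallest n for 95% at 3%: ln(0.05) / ln(0.97) = 98.4, so 99 subjects.
- Subject-days: 100 × 42 = 4200, which is 600 weeks or 11.5 years. This is also confirmed.

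**Step 2. Count the subjects by type of exposure in Stage I.**
- Implant, surgery, device, and any stimulation including the blinding pulses: both arms, 100 to 120.
- Therapeutic VNS: the VNS arm only, about 50 to 60.

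**Step 3. Apply the same formula to each count.** The lowest rate detected with 95% probability is 1 − 0.05^(1/n). This is also the one-sided 95% upper limit for the rate when no event is seen.

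| n | Who | P(at least one event at 3%) | Rate detected with 95% probability |
|---|---|---|---|
| 120 | all implanted, maximum | 97.4% | 2.5% |
| 100 | all completers | 95.2% | 3.0% |
| 60 | therapeutic VNS, maximum | 83.9% | 4.9% |
| 50 | therapeutic VNS, completers | 78.2% | 5.8% |

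The chance of missing a 3% stimulation harm altogether is therefore 100 − 83.9 = 16.1% to 100 − 78.2 = 21.8%, against 100 − 95.2 = 4.8% on the SAP's count.

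**Step 4. See what the crossover would have to supply.** The 95% at 3% needs 99 subjects on active VNS.
- With 50 per arm: 99 − 50 = 49 of the 50 controls would have to take the Stage II course.
- With 60 per arm: 99 − 60 = 39 of the 60.

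Neither contribution is part of the Stage I data.

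**The case against.** The case for leaving Section 3.4 alone has four parts.

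1. *Controls do receive VNS.* Each control gets four pulses at every visit, so calling all 100 subjects recipients of VNS is literally true. This stands. A reader might infer that the 95% figure fits implant harms only, but the SAP does not support that: the count of 100 also covers device events and anything caused by the low-dose blinding stimulation. It does not cover the therapeutic dose.

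2. *The 95% statement speaks of the study, not of Stage I.* Section 3.3 has the control group begin a 6-week course with active VNS in Stage II, so about 100 subjects could eventually have an active course. This stands as a possible reading, and on it the figure could be right. It does not rescue the figure for this SAP. Section 3.3 leaves continuation in Stage II to the investigator and the subject, that stage is unblinded, and Section 3 assigns it to a later plan. Section 3.4 does not say that its count relies on crossover.

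3. *The 4200 subject-days are implanted follow-up time.* This stands. It is tempting to infer that the true exposure is half the stated figure, but the documents do not support that contrast. The sentence counts implantation and follow-up and does not mention stimulation. Halving it would also ignore the VNS arm's daily home magnet use in the following 90 days. If each of those days counted, 50 subjects × (42 + 90) days would give 6600 days and 60 subjects would give 7920, both above 4200. Longer exposure of the same people does not raise their number, so the subject-count result is unaffected.

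4. *Nothing in the analysis depends on it.* Section 5.13.1 tabulates adverse events by treatment group, so readers of the results will see the VNS-arm denominator. No safety hypothesis or success criterion uses the 3%, and the sample size is supported separately by the efficacy calculations. All of this stands, and it keeps the point minor.

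**Conclusion.** The point holds in limited form. The arithmetic in Section 3.4 is correct, and so is its conclusion for implant, surgery, device and blinding-stimulation events. For therapeutic-dose stimulation harms in Stage I the denominator is about 50 to 60, not 100. Detection at a 3% rate is 78% to 84% rather than 95%, and 95% is reached only for rates of about 5.8% to 4.9%. Across the whole study, the claim of about 100 subjects on active VNS depends on most controls taking an optional course, and on nearly all of them if the total is 100.

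This rests on three assumptions: arms of equal size, 50 to 60 VNS-arm subjects actually starting stimulation, and a common, independent per-subject event risk.

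The point concerns the stated safety precision for one of two named targets. It does not show that the trial is too small, that exposure time is overstated or that any planned analysis is wrong. The change is worth considering and is not essential.

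**What to change.** Replace the single safety sentence in Section 3.4 with two:

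1. For implant, surgery, device and any-stimulation events, 100 to 120 subjects give at least a 95% probability of observing an event with a true rate of 3%.
2. For therapeutic VNS in Stage I, about 50 to 60 subjects give a 78% to 84% probability at 3%, and 95% only for rates of about 5% to 6% or more. Reaching about 100 subjects on active VNS depends on controls taking the Stage II crossover course, which falls under the later plan.

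Label the 4200 subject-days as implanted follow-up time over both arms.

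The cost is a few lines of text, with no new data, tables, analyses or subjects. The downside is that the stated safety precision for stimulation will look weaker than it does now.

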3.5 Futility Analysis

A futility analysis will be conducted by the DSMB when 40 subjects have completed 6-weeks of rehabilitation and post-1 assessment at Visit 5. The conditional power of the two-sample test comparison between the two treatment groups be calculated to determine the futility index (1 – conditional power). The study will be assessed for stopping if the futility index is greater than 0.90 (at approximately $t < -1.25$).

4 ANALYSIS SETS & SCHEDULE

4.1 Intent to Treat (ITT)

The ITT population will include any subject who is randomized, and will be the basis of the efficacy and safety analyses. All subjects who undergo surgery will be included in the safety population, with all adverse event and safety information reported.

4.2 Per Protocol (PP)

The PP will include subjects who are compliant with at least two-thirds of therapy sessions completed during the 6 week period, and do not have major protocol violations that could impact and/or compromise the safety or efficacy of the treatment. Treatment assignment in the Per Protocol population will be as treated, not as randomized. An initial assessment of exclusion from the Per Protocol population will be made as soon as possible prior to the end of Stage I (which is the earliest it can occur); all exclusion from the Per Protocol population will be finalized prior to database lock. All protocol violations will be documented in the study files, and any significant violations will be included in the study report.

4.3 Other Analysis Populations (Including Subgroups)

Other populations and analyses may be conducted at the discretion of MicroTransponder, Inc. to supplement the results or for research purposes. Preliminary subgroups include gender, region, Baseline FM score, stroke volume (based on MRI), CST integrity (based on MRI). Other subgroups may be performed based on indications from initial data analyses. All critical subgroup analyses will be specified prior to unblinding, although others may be added as indicated.

4.4 Schedule

The table below indicates the primary, secondary, and other analysis timepoints and measures. The change between each visit and the pre-therapy baseline (V4) is the measure of interest, and the difference between the two treatment groups will be analyzed. Within-group changes will also be analyzed.

	Visit 5 (One day after 6-weeks of therapy)	Visit 7 (90 days after 6-weeks of therapy)	Long-Term (6,9,12m after 6-weeks of VNS) Or (LT4, LT5, LT6)	Crossover (Control one day after 6-weeks of VNS [LT1] compared to V7 (prior to start of VNS))
	UEFM Change (primary)	UEFM Response (2 nd)	UEFM Change (o)	UEFM Change (o)
	UEFM Response (o)	UEFM Change (2 nd)	UEFM Response (o)	UEFM Response (o)
	WMFT (o)	WMFT (2 nd)	WMFT (o)	WMFT (o)
	QOL (o)	QOL (o)	QOL (o)	QOL (o)
	BDI (o)	BDI (o)	BDI (o)	BDI (o)
	MAL (o)	MAL (o)	MAL (o)	MAL (o)

o = other (not a primary or secondary analysis)

UEFM – Upper Extremity Fugl-Meyer; WMFT – Wolf Motor Function Test

MAL – Motor Activity Log; QOL includes SIS, SS-QOL, 5Q-5D

BDI – Beck Depression Inventory (assessed as both an efficacy and a safety measure)

5 STATISTICAL METHODOLOGY AND ANALYSES

5.1 General Considerations

All descriptive summaries will be reported by treatment group. All summaries of continuous data will be presented as means (SD), and/or with medians with min/max as appropriate. Count data will be presented as number within each treatment group and % of subjects within each group. 95% confidence intervals will also be provided for the efficacy endpoints. All unscheduled assessments will be excluded from summary tables. Data from unscheduled assessments will be displayed in listings.

In Stage I, the control subjects will be compared against the active VNS subjects, with null hypothesis of equal change from baseline (Visit 4) in the FMA UE score between the two groups. For the control subjects in Stage II, Day 1 post treatment (LT1) will be compared against Visit 7 (end of randomization/Stage I) to determine treatment effect, with null hypothesis that there is no change from Visit 7 to LT1. All data analyses and statistical testing will be conducted using SAS Version 9.4 or higher. Unless specified for a specific test, a significance level of $\alpha = 0.05$ will be used.

Analyses outside of this SAP maybe performed to supplement results or for research purposes at the discretion of MicroTransponder, Inc.

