Stage II: Stage II begins after Visit 7 (Day 90 post treatment). It will be the Investigator's and subject's decision to continue treatment during this unblinded follow-up stage. The intent is that all subjects will be followed through at least 12 months of post-acute study. All original VNS group subjects continue at-home rehabilitation and home-initiated stimulation for 30 minutes daily and all original Control group subjects start a 6-week rehabilitation session plus active VNS. The assessments at Visit 7 will serve as Baseline for Stage II. The control subjects will have 6 weeks of rehabilitation sessions plus active VNS treatment, followed by assessment Visits LT1 (Day 1 after the 6 week treatment), LT2 (Day 30 post treatment) and LT3 (Day 60 post treatment; at Month 3 of Stage II). All subjects will then have Visits LT4 (Month 6 of Stage II) LT5 (Month 9) and LT6 (Month 12). Different stimulation settings may be tried during the long-term therapy, especially in non-responders (those with less than a 6-point FMA-UE change).

Study guidelines allow subjects to continue at-home stimulation for 30 minutes a day while performing rehabilitation movements at home, as designated by the therapist.

All continuing subjects will have two more in-clinic rehabilitation sessions with VNS for one week (“booster sessions”), approximately one month prior to LT4 (Month 6), and LT6 (Month 12) assessments. Subjects will also be able to utilize daily subject-initiated stimulation during in-home rehabilitation.

Stage III: After Stage II of VNS therapy, subjects who wish to continue VNS use must have at least annual follow-up visits. Those who do not have annual visits or who wish to discontinue will have their device systems explanted.

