5.14 Long Term Follow-up

A separate Analysis Plan defining specific comparisons of interest will be developed prior to the first subject completing Stage II (one year of VNS). Data from Stages II and III, long term follow-up, will be summarized by the original treatment group assignment. For the control group, the FM-A change from Visit 7 (end of Stage 1), to Visit LT1 (1 day after VNS treatment), will be compared to the change from Visit 4 to Visit 5 with a paired-t test to evaluate the effect of VNS treatment. Maintenance of response, changes over time and after treatment modification will also be summarized with descriptive statistics. Long-term assessments will be collected for as long as the subject receives treatment. However, the key long-term assessments will be provided at 3, 6, 9, and 12 months. The analysis will assess continuation of benefit (maintenance of response and changes over time) on each assessment through the 12-month assessment. Additional exploratory analyses may be performed based on the nature of the follow-up data encountered.

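### The Section 5.1 crossover null of no change from Visit 7 to LT1 cannot separate VNS from the rehabilitation given with it, and Section 5.14 states a different null for the VNS effect

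*SAP*

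**What the plan says.** Section 5.1 sets the Stage II comparison for control subjects as LT1 against Visit 7, "to determine treatment effect, with null hypothesis that there is no change from Visit 7 to LT1". It names no test statistic; the section's default significance level of 0.05 applies. The crossover column of the table in Section 4.4 uses the same contrast and labels every measure in it as other, that is, neither primary nor secondary.

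Section 3.3 describes what happens on either side of Visit 7. In the 90 days before it, "subjects will not receive in-clinic rehabilitation, but are given a magnet to swipe" before home exercise, and in control subjects the magnet does not activate VNS. After it, "The control subjects will have 6 weeks of rehabilitation sessions plus active VNS treatment", with LT1 one day after that course ends.

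Section 5.14 gives another crossover test. For the control group, the Visit 7 to LT1 change "will be compared to the change from Visit 4 to Visit 5 with a paired-t test to evaluate the effect of VNS treatment".

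Section 3.4 gives the planning value for six weeks of rehabilitation without therapeutic VNS, "with control having an average change of 5.2 from baseline".

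**The concern.** In-clinic rehabilitation and active VNS both start after Visit 7 in the control group. A pre-post contrast over that interval measures their joint effect and has no comparator that would isolate VNS. The SAP itself expects rehabilitation without therapeutic VNS to raise the FMA-UE score, so its own planning figure predicts rejection of no change even if VNS adds nothing.

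The SAP also puts two nulls to what reads as one question. In 5.1 the null is a change of zero; in 5.14 it is a change equal to the subject's own Stage I change. The two can give opposite answers: if the second course produces the same gain as the first, 5.1 rejects and 5.14 does not. With no rule on which governs, the later Stage II plan would inherit both, and the more favourable could be chosen after the Stage I results are known.

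**Working it through.** **Inputs from the SAP.** Section 3.4: 50 subjects per group, SD 4.0, control gain 5.2, VNS gain 7.5, difference 7.5 − 5.2 = 2.3, alpha 0.05, 80% power. Section 5.4: two-sided testing for the primary endpoint.

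**Assumptions not in the SAP.** All 50 control subjects enter the crossover (40 also shown). The SD of the Visit 7 to LT1 change is 4.0 (6 also shown). The 5.2-point gain is a first-course planning value, so its use for a second course is an assumption, and smaller gains are shown. The 5.1 comparison is run as a two-sided one-sample t-test on the change.

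**The SAP's own figure.** The standard error of the group difference is 4.0 × √(2/50) = 0.80, and 2.3 / 0.80 = 2.875. Power is Φ(2.875 − 1.96) = 0.82; the noncentral t with 98 df gives 0.81. The stated 80% is reproduced.

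**The 5.1 test when VNS does nothing.** The standard error of the mean change is 4.0 / √50 = 0.566. The noncentrality is the gain divided by 0.566: 5.2 / 0.566 = 9.2; 2.0 / 0.566 = 3.5; 1.0 / 0.566 = 1.8. The probability of rejecting no change is:

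| Second-course rehabilitation gain | n=50, SD 4 | n=50, SD 6 | n=40, SD 4 | n=40, SD 6 |
|---|---|---|---|---|
| 5.2 (as assumed for the first course) | about 100% | about 100% | about 100% | above 99% |
| 2.6 (half) | 99.5% | 85% | 98% | 76% |
| 2.0 | 93% | 64% | 87% | 54% |
| 1.3 (a quarter) | 62% | 32% | 52% | 27% |
| 1.0 | 41% | 21% | 34% | 18% |

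In every row the null of no change is false, because rehabilitation has moved the score. The figures are therefore the power to detect a rehabilitation gain that would then be read as a treatment effect.

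**The 5.14 test.** The within-subject difference is (Visit 7 to LT1 change) − (Visit 4 to Visit 5 change), with SD 4.0 × √(2(1 − ρ)), where ρ is the assumed correlation between the two changes. With equal rehabilitation gains and no VNS effect, the expected difference is 0 and the rejection probability is 5%. With equal gains and a true 2.3-point VNS increment, power at n=50 is 71%, 80%, 90% and 98% for ρ = −0.25, 0, 0.25 and 0.5.

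**Its weakness.** If the second course gives half the rehabilitation gain, a true 2.3-point VNS effect appears as 2.6 + 2.3 − 5.2 = −0.3. If VNS then has no effect, the expected difference is 2.6 − 5.2 = −2.6. At ρ = 0, the test would reject against VNS with probability 89%.

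**The case against.** The strongest reply is scope. The SAP confines itself to Stage I data (Sections 1 and 3), and Section 5.14 leaves the specific Stage II comparisons to a separate plan. The 5.1 sentence is a one-line preview, the crossover measures are labelled other, Stage II is unblinded, and the hierarchy in Section 5.4 does not include them. This stands and limits the consequence. It does not remove a stated null whose result is called the treatment effect.

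A second reply is that the two tests can coexist. Section 4.4 says that within-group changes will be analysed, and Section 3 defines study treatment as VNS delivered during rehabilitation, so treatment effect in 5.1 could mean the effect of the combined course. That reading is possible, and the two analyses are not mutually exclusive. But 5.1 neither says this nor refers to 5.14, and a pre-post change without a comparator is weak evidence even for the combined course.

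A third reply is that 5.14 already contains the better test. It does, which is why the remedy is small. It is not a clean test, because it relies on equal rehabilitation gains in both courses.

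A reader might also infer that 5.1 inflates the type I error above 5%, or opens a false-positive route to an efficacy claim. The documents support neither. The rejected null is truly false, so the fault is attribution, and no section attaches an efficacy claim to this comparison.

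**Conclusion.** The point holds as a defect of attribution and of consistency. The 5.1 contrast cannot identify a VNS effect, 5.14 poses a different null for that effect, and the SAP does not say which governs. That conclusion follows from the treatment schedule and needs no numerical assumption.

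The size does rest on assumptions: the second-course gain, the SD of the Visit 7 to LT1 change, and the number of control subjects who cross over. At n=50 and SD 4.0 the chance of misattribution runs from 41% at a 1-point gain to about 100% at 5.2 points; at n=40 and SD 6 it runs from 18% to above 99%.

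The reach is limited. The Stage I primary and secondary tests and the sample size are untouched. This is a correction that should be made, not a threat to the trial's main result.

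**What to change.** In Section 5.1, remove the statement that the Visit 7 to LT1 comparison determines treatment effect, and remove the no-change null. Report that change with a 95% CI as a descriptive within-group change under rehabilitation plus VNS, and describe the Section 4.4 crossover column in the same way. Refer to the Section 5.14 paired comparison as the crossover test of the VNS effect.

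In Section 5.14, add a sentence that the test is supportive only, because course order is confounded with treatment, and that a smaller rehabilitation gain in the second course would bias it against VNS. Carry the same wording into the Stage II plan.

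The cost is SAP wording: no new data, visits or subjects. The downside is a crossover result likely to look less favourable than the test against zero, with a possible bias against VNS that the sponsor would have to explain.
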